5.3.2.1. Analysis Methods

5.3.2.1.1. Primary Analysis

The verbatim terms used in the case report form by investigators to identify AEs will be coded using the Medical Dictionary for Regulatory Activities (MedDRA). Any AE occurring at or after the initial administration of study intervention in Study 54315419TRD3013 through completion the participant's 2-week safety follow-up visit in Study 54135419TRD4010 is considered to be treatment emergent. Serious AEs reported within 30 days after the last dose of study intervention in Study 54135419TRD4010 are also regarded as treatment emergent. If the event occurs on the day of the initial administration of study intervention, and either event time or time of administration are missing, then the event will be assumed to be treatment emergent. If the event date is recorded as partial or completely missing, then the event will be considered to be treatment emergent unless it is known to be prior to the first administration of study intervention based on partial onset date or resolution date. All reported treatment-emergent AEs will be included in the analysis. For each AE, the number, proportion and incidence rate of participants who experience at least 1 occurrence of the given event will be summarized. The incidence rate is defined as the numbers of participants who experience at least 1 occurrence of the AE divided by the time at risk. Time at risk is defined as time from initial administration of study intervention in Study 54135419TRD3013 until first occurrence of AE or until last dose of study intervention plus 30 days (if participant did not experience AE). To calculate time at risk if the start date of an AE is missing completely or partially, following imputation rule will be applied:

If the onset date of an adverse event is missing day only, it will be set to:

- i) First day of the month that the AE occurred, if month/year of the onset of AE is different than the month/year of initial dosing date of Study 54135419TRD3013
- ii) The day of initial dosing in Study 54135419TRD3013, if the month/year of the onset of AE is the same as month/year of the initial dose date and month/year of the AE resolution date is different
- iii) The day of initial dosing in Study 54135419TRD3013 or day of AE resolution date, whichever is earliest, if month/year of the onset of AE and month/year of the initial dosing date of Study 54135419TRD3013 and month/year of the AE resolution date are the same.

If the onset date of an adverse event is missing both day and month, it will be set to the earliest of:

- i) January 1 of the year of onset, as long as this date is after the initial dosing date of Study 54135419TRD3013.
- ii) one day after initial dosing date in Study 54135419TRD3013, if this date is the same year that the AE occurred.

A completely missing onset date of an adverse event will be set to the initial dosing date in Study 54135419TRD3013.

If the end date of an AE that is not recorded as ongoing is missing completely or partially, following imputation rule will be applied:

- For AEs with outcome Fatal, the AE end date is the death date
- The missing day of resolution of an adverse event will be set to the last day of the month of resolution.
- If the resolution date of an adverse event is missing both day and month, it will be set to the earlier of the date of withdrawal, study completion, or December 31 of the year.
- A completely missing resolution date of an adverse event that is not recorded as ongoing will be set to the date of study completion/discontinuation.

For a total number of participants with treatment-emergent AEs, SAEs,... (not on SOC, PT level), the 95% confidence interval of the proportion and incidence rate will be calculated. For proportion, the 95% Clopper-Pearson confidence interval will be calculated. The 95% confidence interval of the incidence rate will be based on a Poisson model with development of treatment-emergent AE as dependent variable, an intercept and log (time at risk) as offset.

Summary tables will be provided for treatment-emergent AEs:

- AEs
- AEs (SOC, PT level only for most common TEAE) stratified by AE duration
- End date same as start date
- End date later than start date (ongoing AEs to be classified in this group)
- Serious AEs (SAEs)
- AEs leading to discontinuation of each study agent within the study intervention
- AEs by severity
- AEs by relationship to each study agent within the study intervention
- AEs leading to dose interruption/dose modification of each study agent within the study intervention.

In addition to the summary tables, listings will be provided for participants who:

- Had SAEs
- Had AEs leading to discontinuation of study intervention.
- AEs of special interest (Appendix 7)

Incidence of treatment-emergent AEs of special interest will be summarized, grouped in the following MedDRA-based categories: sedation, dissociation, suicidality, suggestive of abuse potential, cystitis and hepatic impairment. See Appendix 7 for a list of AEs in each category.

CONFIDENTIAL – FOIA Exemptions Apply in U.S.

A listing of participants who died will be provided.

Duration of TEAE

Additionally a bar chart will be created to present the duration of AEs (Treatment-emergent AEs in more than 5% of patients).

Duration of AEs will be calculated as:

- If AE start date = AE end date: AE end time AE start time
- If AE start date < AE end date: AE end date AE start date +1
- Note: for AE with outcome FATAL: AE end date= death date

AEs are categorized in following categories

- Duration: <= 1hour
- Duration: > 1 hour to <= 2 hours
- Duration: > 2 hours to <= 3 hours
- Duration: > 3 hours to <= 8 hours
- Duration: > 8 hours but AE start date=AE end date
- Unknown: Missing duration (ie. missing start or end time) and AE start date=AE end date
- Duration: 2 days to <= 7 days
- Duration: 8 days to <=28 days
- Duration: >28 days or AE ongoing

Bar chart that shows the percentage of AEs in each category is created.

Clinically significant weight change

- Calculate the number and % of patients with an increase of at least 7% in body weight at any point in time compared to baseline. Only include visits until last dose + 14 days.
- Calculate the number and % of patients with a decrease of at least 7% in body weight at any point in time compared to baseline. Only include visits until last dose + 14 days.
- Above proportions are calculated on all patients in the safety analysis set who have baseline and at least one post-baseline body weight measurement.
- If body weight missing, assume no 7% increase/decrease from baseline.

Medication

- Calculate the number and % of patients who received any concomitant therapy for TEAE. Denominator is patients in safety analysis set with at least one TEAE.
- Calculate the number and % of patients who received any concomitant therapy for TEAE, by preferred term. Denominator is patients in safety analysis set who developed the specific preferred term as TEAE.

• Analyses are based on data on AE page (AECONTRT). If AECONTRT is missing, assume no concomitant therapy received.

Days with AE

- For each patient, calculate the number of days on which the patient had any TEAE, including only days from date of first dose of study intervention until date of last dose of study intervention inclusive. If at a certain day the patient had multiple TEAEs, this should be counted as one day. Report summary statistics (mean, SD, median, range).
- Divide the number calculated above by study intervention duration (date of last dose of study intervention date of first dose of study intervention +1). Report summary statistics (mean, SD, median, range).
- For AEs that are ongoing (AEENRF=AFTER): AE end date will be set as date of study completion/discontinuation

TEAEs that led to dose reduction

- Calculate percentage of TEAEs that led to dose reduction: denominator is all TEAEs. Numerator is all TEAEs with action 'Dose Reduced' (AEACNS1/AEACNS2).
- Calculate percentage of TEAEs that led to dose reduction, by PT: denominator is all TEAEs
 of specific PT. Numerator is all TEAEs of specific PT with action 'Dose Reduced'
 (AEACNS1/AEACNS2).

TEAEs on dosing days

- Calculate percentage of TEAEs that occurred on dosing days, in total and on PT level
- Of TEAEs that occurred on dosing days, calculate the percentage with same day resolution, in total and on PT level.

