8.3. Adverse Events, Serious Adverse Events, and Other Safety Reporting

Timely, accurate, and complete reporting and analysis of safety information, including adverse events, serious adverse events, and PQC, from clinical studies are crucial for the protection of participants, investigators, and the sponsor, and are mandated by regulatory agencies worldwide. The sponsor has established Standard Operating Procedures in conformity with regulatory requirements worldwide to ensure appropriate reporting of safety information; all clinical studies conducted by the sponsor or its affiliates will be conducted in accordance with those procedures.

Adverse events will be reported by the participant (or, when appropriate, by a caregiver, surrogate, or the participant's legally acceptable representative) for the duration of the study.

For study intervention that meets the definition of a combination product, malfunctions or deficiencies of a device constituent will be reported as PQC.

Further details on adverse events, serious adverse events, and PQC can be found in Appendix 5, Adverse Events, Serious Adverse Events, Product Quality Complaints, and Other Safety Reporting: Definitions and Procedures for Recording, Evaluating, Follow-Up, and Reporting.

8.3.1. Time Period and Frequency for Collecting Adverse Event and Serious Adverse Event Information

All Adverse Events

All adverse events and special reporting situations, whether serious or non-serious, will be reported from Day 1, starting after the first dose of esketamine nasal spray, until completion of the participant's 2-week safety follow-up visit. Prior to the first dose in this long-term extension, this information will be captured as part of Study TRD3013.

Serious Adverse Events

All serious adverse events, as well as PQC, occurring during the study must be reported to the appropriate sponsor contact person by study-site personnel within 24 hours of their knowledge of the event.

Serious adverse events, including those spontaneously reported to the investigator within 30 days after the last dose of study intervention, must be reported. The sponsor will evaluate any safety information that is spontaneously reported by an investigator beyond the time frame specified in the protocol.

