9.4.5. Safety Analyses

All safety analyses will be made on the Safety/Efficacy Population.

Adverse Events

The verbatim terms used in the eCRF by investigators to identify adverse events will be coded using the Medical Dictionary for Regulatory Activities (MedDRA). Any AE occurring at or after the initial administration of study intervention through the day of last dose plus 30 days is considered to be intervention-emergent. All reported intervention-emergent adverse events will be included in the analysis. For each adverse event, the percentage of participants who experience at least 1 occurrence of the given event will be summarized.

Intervention-emergent AEs of special interest will be summarized separately grouped in the categories as described in Section 8.3.6.

Summaries, listings, or participant narratives may be provided, as appropriate, for those participants who die, who discontinue intervention due to an adverse event, or who experience a serious adverse event.

Clinical Laboratory Tests

Only clinically relevant changes in laboratory parameters that meet the definition of an AE during the study are reported by the investigator as AEs and these will be included in the all intervention-emergent AE analyses.

Vital Signs

Descriptive statistics of pulse/heart rate, respiratory rate, and supine blood pressure (SBP and DBP) values and changes from Study TRD3013 baseline will be summarized at each scheduled time point. The percentage of participants with values beyond clinically important limits will be summarized.

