5.3.2. Estimand for treatment-emergent adverse events

Primary Trial Objective: To assess the long-term safety and tolerability of esketamine nasal spray in combination with an SSRI/SNRI in participants who have completed 32 weeks of esketamine nasal spray treatment in Study 54135419TRD3013.

Estimand Scientific Question of Interest: What is the safety and tolerability of esketamine nasal spray in combination with an SSRI/SNRI in participants who have completed 32 weeks of esketamine nasal spray treatment in Study 54135419TRD3013, based on the development of treatment-emergent adverse events (AEs)?

The estimand is defined by the following 5 components:

Study Intervention: esketamine nasal spray in combination with an SSRI/SNRI

Population: participants who have completed 32 weeks of esketamine nasal spray treatment in Study 54135419TRD3013 and received at least one dose of esketamine in Study 54135419TRD4010

Variable: development of treatment-emergent AE: from the initial administration of study intervention in Study 54135419TRD3013 through the day of last dose in Study 54135419TRD4010 plus 30 days

Summary Measure: number and incidence of subjects who develop an treatment-emergent AE per person-time at risk

Intercurrent events and their corresponding strategies:

	Name of Strategy for Addressing Intercurrent
Intercurrent Events	Events and Its Description
	While on treatment: All AEs occurring through
intervention for any reason	the day of last dose plus 30 days are included in
	analysis
Withdrawal from the study	While on treatment: Same as above

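### Non-serious TEAE rates stop counting events at the 2-week follow-up visit but give event-free participants time at risk to last dose + 30 days, so these rates run slightly low

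*SAP*

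**What the plan says.** Treatment-emergent adverse events are a primary endpoint (SAP 5.3.1), and the estimand summarises them per person-time at risk. The documents end the window in two ways.

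**At the follow-up visit, with 30 days for serious events only**
- SAP 5.3.2.1.1: events from the first TRD3013 dose "through completion the participant's 2-week safety follow-up visit in Study 54135419TRD4010 is considered to be treatment emergent". It adds: "Serious AEs reported within 30 days after the last dose of study intervention in Study 54135419TRD4010 are also regarded as treatment emergent".
- Protocol 8.3.1: adverse events are collected "until completion of the participant's 2-week safety follow-up visit". For serious events: "Serious adverse events, including those spontaneously reported to the investigator within 30 days after the last dose of study intervention, must be reported".

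**At last dose + 30 days for everything**
- SAP 5.3.2, estimand variable: "through the day of last dose in Study 54135419TRD4010 plus 30 days". The intercurrent-event strategy repeats this for all AEs.
- SAP 5.3.2.1.3, extension-only selection: also last dose + 30 days.
- Protocol 9.4.5: any AE "through the day of last dose plus 30 days is considered to be intervention-emergent".
- SAP 5.3.2.1.1, time at risk: "until first occurrence of AE or until last dose of study intervention plus 30 days (if participant did not experience AE".

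The follow-up visit falls 14 ± 2 days after the last session (Protocol 1.1 and Schedule of Activities). SAP Appendix 2 lists only the dropped interim analysis as a change from the protocol.

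**The concern.** Within SAP 5.3.2.1.1, the rule for what counts as an event and the rule for time at risk end at different points. Between the follow-up visit and day 30, a participant without the event accrues person-time, but a non-serious event in that interval is neither routinely collected nor treatment-emergent. Unobserved days are counted as observed and event-free, which can only lower the rate. The same time at risk is the offset in the Poisson model, so the confidence interval for the total rates is affected too.

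The window itself is also ambiguous. If a non-serious event on day 20 were recorded after a day-14 visit, it would be treatment-emergent under the estimand, SAP 5.3.2.1.3 and Protocol 9.4.5, but not under the primary analysis text. Two programmers could derive different primary-endpoint counts from the same data.

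**Working it through.** The documents state no rate or precision figure for this endpoint, so there is nothing to reproduce.

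**Inputs.** Follow-up visit at day 14 ± 2 after last dose; time at risk to day 30 for event-free participants (SAP 5.3.2.1.1); time at risk starting at the first TRD3013 dose (same section); 32 weeks of parent-study treatment, taken as 224 days; up to 104 extension weeks, or 728 days (SAP 1.2); expected enrolment of 100 to 200 (SAP 3). The 52-week, 26-week and one-dose durations are assumptions, chosen because participants leave once commercial supply becomes accessible locally.

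**Step 1: the gap.** 30 − 14 = 16 days; 30 − 16 = 14 and 30 − 12 = 18 at the edges of the visit window. If everyone is event-free, the excess is 100 × 16 / 365.25 = 4.4 person-years, or 8.8 for 200 participants.

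**Step 2: ceiling in the pooled primary analysis.** Let D be the days from first TRD3013 dose to last dose. For a very rare event almost everyone is event-free, and the understatement is 1 − (D + 14)/(D + 30) = 16/(D + 30).

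| Extension treatment | D | D + 30 | 16/(D + 30) |
|---|---|---|---|
| 104 weeks | 952 | 982 | 1.6% |
| 52 weeks | 588 | 618 | 2.6% |
| 26 weeks | 406 | 436 | 3.7% |
| About one dose | 224 | 254 | 6.3% |

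**Step 3: events that are not rare.** A participant with the event stops accruing time at first occurrence, so only the event-free fraction adds the 16 days. With constant hazard λ and cumulative risk p by T = D + 14: λ = −ln(1 − p)/T, mean observed time = p/λ, added time = 16(1 − p), and understatement = added / (observed + added).

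- D = 952, p = 10%: observed 916.9 days, added 14.4; 14.4/931.3 = 1.5%. The rate is 3.92 instead of 3.98 per 100 person-years.
- D = 952, p = 50%: 8.0/704.8 = 1.1%.
- D = 952, p = 90%: 1.6/379.2 = 0.4%, or 86.69 instead of 87.06 per 100 person-years.
- D = 588, p = 10%, 50%, 90%: 2.5%, 1.8%, 0.7%.
- D = 224, p = 10%, 50%, 90%: 6.0%, 4.5%, 1.7%.

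**Step 4: extension-only rates.** If the denominator restarted at the first TRD4010 dose, the ceilings would be 16/758 = 2.1% (104 weeks), 16/394 = 4.1% (52 weeks) and 16/212 = 7.5% (26 weeks). SAP 5.3.2.1.3 selects events and lists outputs but defines no restarted denominator, so these figures are conditional.

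**Step 5: when the gap is not 16 days.** A withdrawal visit held at least 14 days after the last dose serves as the follow-up visit, with no upper limit (Schedule of Activities, footnote e). The gap then shrinks, and after day 30 it reverses: events would be counted beyond the end of time at risk. If no follow-up visit takes place (consent withdrawn, lost to follow-up), the gap can reach 30 days. For such a participant with full exposure the share is 30/982 = 3.1%.

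**Step 6: what is not affected.** SAE rates use + 30 days in both numerator and denominator. Proportions have no person-time denominator.

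**The case against.** The strongest reply is that the effect is trivial. The study is single-arm and descriptive, with no hypothesis, comparator or rate threshold, so a relative change of roughly 0.4% to 2.6% at one to two years of extension treatment alters no conclusion. Protocol 9.4.5 asks only for percentages, which have no denominator mismatch. SAP 5.3.2.1.1 gives confidence intervals only for totals, and the overall TEAE proportion may well be high, which is where the understatement is smallest. All of this stands, and it limits the point to a small bias and an unreconciled definition.

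A second reply is that the estimand targets the period to + 30 days, so the true bias is the number of events missed after the visit. Protocol 2.2.3.4 reports that most events came shortly after dosing and resolved the same day, so few may be missed. This also stands in part: treating the person-time share as bias against that target assumes that the hazard off drug equals the hazard on drug. It does not rescue the text, because the non-serious events needed to estimate a rate to + 30 days are not collected.

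A reader might infer that every TEAE rate is diluted by 16 days per participant, or that early leavers lose 7.5% in the primary analysis. The documents support neither. SAE rates match by definition, although capture after the visit may depend on spontaneous reports. Participants with the event add no such days. The primary denominator carries about 32 weeks of TRD3013 time for everyone, so the 26-week ceiling is 3.7%.

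**Conclusion.** The point holds for TEAE rates other than SAE rates. The windows for counting non-serious events and for time at risk differ by nominally 16 days per event-free participant. No section reconciles them, and Appendix 2 does not declare the departure from Protocol 9.4.5. At the nominal gap the direction is downward and the size is small: in the pooled primary analysis, at most about 1.6% with full exposure and about 6% for exit just after entry, and less for common events. These sizes rest on a constant hazard, a day-14 visit and the assumed exposure durations. The bias would not by itself change a conclusion. The case for correcting it is that a primary-endpoint rule contradicts its own estimand and its error favours the product, while the repair uses data already collected.

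**What to change.** Use one window per event class for both numerator and denominator.

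- **Any-TEAE and all rates other than SAE rates:** count events, and end time at risk, at the earliest of first event, the actual safety follow-up visit and last dose + 30 days. If there is no follow-up visit, use the date of last contact or withdrawal in its place. Otherwise the rule defaults to + 30 days in the participants with the largest gap.
- **SAE rates:** keep last dose + 30 days. A serious event after the cut-off above counts only in the SAE rates. Otherwise it would enter the any-TEAE numerator after that participant's risk time had closed.
- **Alignment:** write these windows into SAP 5.3.2, 5.3.2.1.1 and 5.3.2.1.3, state where the denominator starts in the extension-only analysis, and list the departure from Protocol 9.4.5 in Appendix 2.

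The SAP already ends time at risk at the last visit date for relapse (5.4.1.2) and for vital signs (5.6.3.2), so the approach is not new to it. The cost is SAP wording, one extra derivation and slightly less favourable rates. No new data are needed.

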4.2. Justification for Dose

All participants will receive flexible doses (either 28 mg [elderly participants and adults of Japanese ancestry only], 56 mg, or 84 mg) of esketamine nasal spray, based on their tolerability and response to esketamine in Study TRD3013.

The dose selections used in this study are in line with previous Phase 2 and Phase 3 studies where esketamine was administered at doses of 28 mg, 56 mg, or 84 mg. Phase 1 and 2 studies in elderly and Japanese participants, which indicated higher mean plasma esketamine C_{max} and AUC_{∞} values at studied doses, support the dose of 28 mg in these 2 populations. A flexible dosing schedule was used in Phase 3 studies (TRD3002, TRD3004, and TRD3005) to facilitate improved tolerability by gradually increasing the dose higher and to align with clinical practice, as many clinicians prefer to gradually increase the dose of AD medication and then adjust as clinically required. Based on the approved SmPC for esketamine nasal spray, this study is being conducted with a flexible dosing scheme.

In the longer-term Phase 3 studies (TRD3003 and TRD3004), the frequency of nasal dosing after the induction phase was individualized to once weekly or every other week to achieve the lowest dosing frequency for an individual participant that could sustain initial improvements in depressive symptomatology. Data from the up-to-9-week open-label phase of Study TRD2003 showed that reducing the dosing frequency from twice-weekly to weekly or every other week did not impact the ability to maintain the AD activity of esketamine.

Background Medication: SSRI/SNRI

All participants must be continuing their same SSRI/SNRI as during Study TRD3013 on Day 1 to be eligible for the study. Participants must be taking an SSRI/SNRI that is approved for use in depression in their country of participation; off-label use of any SSRI/SNRI is not permitted. The continuing SSRI/SNRI dosage may be optimized throughout the study, at the investigator's discretion and based on the SmPC (or local equivalent, if applicable). During this long-term extension study, investigators will be allowed to switch individual participant's SSRI/SNRI for tolerability issues (see Section 6.1.5 for additional details).

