5.1. Inclusion Criteria

Each potential participant must satisfy all of the following criteria to be enrolled in the study:

- 1. completed the maintenance phase (Week 32) of Study TRD3013 and had esketamine nasal spray in combination with continuing SSRI/SNRI administered through Week 30 (every 2 week dosing) or Week 31 (once weekly dosing) of Study TRD3013, and continues to be willing to be treated with esketamine nasal spray.
- 2. must, in the opinion of the investigator, be benefiting from continuation of esketamine nasal spray in combination with their current SSRI/SNRI based on efficacy and tolerability assessed on Day 1 of this study.
- 3. must be medically stable based on the investigator's judgment.
- 4. must sign an ICF indicating that he or she understands the purpose of, and procedures required for, the study and is willing to participate in the study.
- 5. a woman of childbearing potential must have a negative urine pregnancy test on Day 1.
- 6. a woman must be (as defined in Appendix 2, Contraceptive and Barrier Guidance)
 - a. Not of childbearing potential
 - b. Of childbearing potential and
 - Practicing a highly effective, preferably user-independent method of contraception (failure rate of <1% per year when used consistently and correctly) and agrees to remain on a highly effective method while receiving study intervention and until at least 6 weeks after last dose the end of relevant systemic exposure. The investigator should evaluate the potential for contraceptive method failure (eg, noncompliance, recently initiated) in relationship to the first dose of study intervention. Examples of highly effective methods of contraception are located in Appendix 2, Contraceptive and Barrier.
- 7. male participants who are sexually active with a woman of childbearing potential must agree to the following during the intervention period and for at least 1 spermatogenesis cycle (defined as approximately 90 days) after receiving the last dose of study intervention (ie, esketamine nasal spray), must fulfill the following criteria:
 - must be practicing a highly effective method of contraception with his female partner.
 - must use a condom if his partner is pregnant.
 - must agree not to donate sperm.

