4. POPULATIONS (ANALYSIS SETS) FOR ANALYSIS

Analysis Sets	Description
Enrolled	All participants who sign the ICF
Safety/Efficacy	All participants who received at least 1 dose of esketamine anytime during the 54135419TRD4010 study.

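### The pooled rate of AEs leading to discontinuation includes 32 parent-study weeks that the entry rules leave essentially event-free, and no matching extension-only rate is specified

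*SAP*

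**What the plan says.** Rates: SAP 5.3.2.1.1 states "For each AE, the number, proportion and incidence rate of participants who experience at least 1 occurrence of the given event will be summarized". The denominator rule is "Time at risk is defined as time from initial administration of study intervention in Study 54135419TRD3013 until first occurrence of AE"; people without the event are counted to 30 days past their last dose. The summary tables listed there include "AEs leading to discontinuation of each study agent within the study intervention". For category totals, given as an open-ended list that starts with AEs and SAEs, "the 95% confidence interval of the proportion and incidence rate will be calculated".

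Who is counted: the Safety/Efficacy set in SAP section 4 is "All participants who received at least 1 dose of esketamine anytime during the 54135419TRD4010 study". The estimand population in SAP 5.3.2 has completed 32 weeks of esketamine in TRD3013 and "received at least one dose of esketamine in Study 54135419TRD4010".

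Entry: inclusion criterion 1 (Protocol 5.1) requires that the person "had esketamine nasal spray in combination with continuing SSRI/SNRI administered through Week 30 (every 2 week dosing) or Week 31 (once weekly dosing"). Protocol 4.2 adds: "All participants must be continuing their same SSRI/SNRI as during Study TRD3013 on Day 1 to be eligible for the study". Exclusion criterion 2 (Protocol 5.2) also removes people who finish TRD3013 with AEs the investigator judges relevant to their safety and well-being.

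Extension-only view: SAP 5.3.2.1.3 selects AEs that start on or after the first TRD4010 dose and lists the outputs to be repeated. Among them are SAEs, AEs of special interest and AEs leading to esketamine interruption or change. AEs leading to discontinuation are not named, and no time at risk is defined.

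**The concern.** A discontinuation AE in TRD3013 would have kept the person out of TRD4010, and so out of the analysis set. The parent weeks are therefore immortal time for this outcome: they enter the denominator, while entry bars almost all matching events from the numerator. The one route left is an AE that began in TRD3013 and ended treatment in TRD4010. Exclusion 2 narrows that route without closing it.

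The rate of AEs that end treatment is a core tolerability result, and long-term tolerability is the primary objective. Protocol 2.2.3.4 reports that such discontinuations were most frequent early in treatment, which is the period that selection removes. A single rate counted from the first TRD3013 dose can be misread as tolerability from the start of treatment. It also understates the rate during the extension.

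The supplementary analysis does not supply the missing figure. The only AE clock in the SAP is the parent-study one. If a programmer carried it over, every extension-only rate would be too low. Selecting by AE start date would also drop the AEs that began in TRD3013 and ended treatment in TRD4010.

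**Working it through.** The documents give no rate or power calculation to reproduce: there is no hypothesis, and the expected 100 to 200 participants is a pragmatic figure. The check applies the SAP's own definition, participants with the event divided by summed time at risk. An intercept-only Poisson model with a log-time offset was fitted and returns exactly that ratio.

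**Inputs from the documents**
- Parent period: 32 weeks, plus a gap g of up to 2 weeks before Day 1 (Protocol 5.5).
- Extension: w = 104 weeks at most, shorter where the drug becomes accessible locally (SAP 1.2).
- Tail: 30 days = 30/7 = 4.29 weeks.

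**Assumptions (not in the documents)**
- Shorter follow-up of 52 or 26 weeks.
- N = 150.
- 2%, 6% or 10% of participants with a discontinuation AE, events spread evenly over 104 extension weeks (mean time 52 weeks).
- 1 year = 52.18 weeks.

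**Step 1. Parent share of time at risk for a person without the event**

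Share = (32 + g) / (32 + g + w + 4.29)

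| w (weeks) | g | Calculation | Share |
|---|---|---|---|
| 104 | 0 | 32/140.29 | 22.8% |
| 104 | 2 | 34/142.29 | 23.9% |
| 52 (assumed) | 0 | 32/88.29 | 36.2% |
| 26 (assumed) | 0 | 32/62.29 | 51.4% |

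**Step 2. Rates with N = 150, w = 104 and d events**

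- Parent person-years (PY) = 150 × 32 / 52.18 = 92.0
- Extension PY = [(150 − d) × 108.29 + d × 52] / 52.18
- Understatement = 92.0 / (92.0 + extension PY)

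| d | Extension PY | Pooled rate per 100 PY | Extension rate per 100 PY | Understatement |
|---|---|---|---|---|
| 3 (2%) | 308.0 | 3/400.0 = 0.75 | 3/308.0 = 0.97 | 23.0% |
| 9 (6%) | 301.6 | 9/393.6 = 2.29 | 9/301.6 = 2.98 | 23.4% |
| 15 (10%) | 295.1 | 15/387.1 = 3.88 | 15/295.1 = 5.08 | 23.8% |

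**Step 3. Carry-over AEs**

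Suppose k of the 9 AEs began at Week 16 of TRD3013 and ended treatment in TRD4010.

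- Pooled PY = [141 × 140.29 + (9 − k) × 84 + k × 16] / 52.18. The understatement, 1 − 301.6 / pooled PY, is 23.1%, 22.9% and 22.6% for k = 1, 2 and 3.
- Selecting by AE start date removes those k events from the extension-only count. They then contribute 52 + 4.29 = 56.29 weeks each without an event. The rate is (9 − k) / {[141 × 108.29 + (9 − k) × 52 + k × 56.29] / 52.18}, which gives 2.65, 2.32 and 1.99 per 100 PY instead of 2.98.

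**Step 4. Shorter follow-up and precision**

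- With 52 weeks of extension follow-up, N = 150 and 8 events at mid-extension (all assumed), the pooled rate is 8/249.2 PY = 3.21 per 100 PY (95% CI 1.61 to 6.42). The extension rate is 8/157.2 PY = 5.09 (2.55 to 10.18).
- With 9 events the Poisson limits are exp(±1.96/√9) = 0.52 and 1.92 times the rate on either clock, because the event count is the same.

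**The case against.** The strongest reply is that the estimand in SAP 5.3.2 declares both the population and the window from first TRD3013 dose, so the pooled rate estimates what it says it estimates. That stands, and it is why the pooled analysis can stay. It does not provide the rate during the extension.

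Second, no sentence gives the discontinuation table a rate by name, and the overall TEAE summary repeated in SAP 5.3.2.1.3 might include a discontinuation row. Both are true. The rate is inferred from the general rule for each AE, the open-ended list of totals and the person-time summary measure. The content of the overall summary is unspecified, and even if it has such a row, no clock is stated for it.

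Third, much of the extension information will be available anyway. Counts, proportions with Clopper-Pearson intervals and the listing do not depend on the clock. Protocol 9.4.5 plans only percentages. Stopping esketamine means leaving the study (Protocol 7.2), and reasons for termination are summarised (SAP 5.2). This limits the damage to the person-time rate.

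Fourth, the bias is small beside the imprecision. With 9 events the extension rate of 2.98 has limits of about 1.55 and 5.72, and 2.29 lies inside them. That is correct, but the bias has a fixed direction, and in a descriptive study the printed rate is itself the result.

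Finally, the 36% and 51% shares and the carry-over cases rest on assumed inputs. Only 22.8% to 23.9% follows from document maxima.

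**Conclusion.** The concern holds. For AEs leading to discontinuation of esketamine or the SSRI/SNRI, the planned pooled rate includes 32 to 34 weeks per person in which entry to the extension rules out essentially all such events. At the 104-week maximum this time is 22.8% to 23.9% of an event-free participant's time at risk, and the rate falls short of the extension rate by about 23% to 24% in the worked examples. If local access shortened follow-up to an assumed 52 or 26 weeks, the share would be about 36% or 51%. Actual follow-up and event counts are not in the documents.

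The conclusion assumes that the discontinuation table carries a rate, which is the natural reading of SAP 5.3.2.1.1. Parent time remains valid risk time for AEs in general. The same reasoning applies in principle to the cardiovascular conditions in exclusion criterion 3, but few events are likely and no dedicated table is planned. This should be corrected before the analysis is run; it does not undermine the other safety results.

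**What to change.** In SAP 5.3.2.1.3:

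- State that time at risk in each supplementary analysis starts and stops with that analysis's AE window. For the extension-only analysis this runs from first TRD4010 dose to first AE in the window, or to 30 days past the last dose.
- Add AEs leading to discontinuation of each study agent to the extension-only outputs. For this output, count events and stop the clock at the date the agent was discontinued, so that AEs that began in TRD3013 and ended treatment in TRD4010 are kept. State this as an exception to the onset-date convention, and say whether an SSRI/SNRI switch for tolerability counts as discontinuing that agent.

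Keep the pooled analysis in SAP 5.3.2.1.1, and label its rates as conditional on completing TRD3013 on both agents and entering TRD4010.

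The cost is SAP wording and one extra output. The planned primary table already needs AEs linked to discontinuation of each agent. Esketamine administrations are recorded in the eCRF (Protocol 6.1), and oral antidepressant dosing is already summarised (SAP 5.6.1), although the programmer should confirm that agent stop dates can be derived. The reported discontinuation rate becomes less favourable; its relative precision does not change.
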